## 8.4 Analyses Plans

### 8.4.1 Analysis Population

All patients who receive at least 1 dose of selinexor will be evaluated for response.

Only those patients who have measurable disease present at baseline, have received at least one cycle of therapy, and have had their disease re-evaluated will be considered evaluable for response. All analyses will be performed with respect to all patients treated

with selinexor, regardless of prior therapy, with a separate analysis performed according to prior treatment status with cohorts of patients as follows:

- (A) Prior abiraterone only
- (B) Prior enzalutamide only
- (C) Prior concomitant therapy with abiraterone and enzalutamide
- (D) Prior sequenced therapy with abiraterone and enzalutamide

#### **8.4.2 Primary Analysis (or Analysis of Primary Endpoints)**

The primary end point is proportion of patients without evidence of radiographic progression at 16 weeks. This is defined from study start until one of the following events occurs:

- $\geq 2$  new bone lesions on Technetium bone scan
- RECIST defined tumor progression
- Cancer related pain requiring opiate analgesics
- Surgery or Radiation to treat a prostate cancer related indication
- Death from any cause

Radiographic PFS will be defined as the time from treatment initiation to the occurrence of either tumor progression in soft tissue according to modified RECIST criteria, identification of new lesions by bone scan ( $\geq 2$  new lesions confirmed  $\geq 12$  weeks later). If no such event exists, then rPFS will be defined as time from start of study until clinical deterioration requiring a change in prostate cancer therapy or at clinician discretion, surgery and/or radiation therapy to treat a prostate-cancer related indication, or death from any cause. PFS will be censored at the last scheduled disease assessment on study. PFS of living patients with no assessment on-study, and PFS of patients with no baseline assessment will be censored at enrollment.

rPFS will be estimated using the Kaplan-Meier product limit method. The median times to event with two-sided 95% confidence intervals will be estimated, together with the estimate of event rates at 6 and 12 months. The score statistic from the cox proportional hazards model will be used in the estimation of the hazard ratio and the associated 95% confidence interval will also be provided.

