### **2.2 Secondary**

- To measure PSA changes at 12 weeks post-selinexor initiation
- To assess time to PSA progression
- To measure time to development of  $\geq 2$  new bone lesions
- To compare the relationship of abiraterone-resistance status (primary vs acquired) and treatment outcome
- To determine the effect of selinexor on persistent pain associated with bone metastasis using the brief pain inventory (BPI) short form.
- To describe the safety profile of selinexor in patients with metastatic castration-resistant prostate cancer.
- To determine the effect of selinexor on circulating leukocyte XPO-1 expression, leukocyte gene expression profile and macrophage inhibitory cytokine-1 (MIC-1) mRNA expression
- To assess serum selinexor trough levels as a function of dose and time since last dose

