### **2.4 Endpoints**

#### **2.4.1 Primary Endpoints**

Radiographic progression free survival (rPFS). This is defined from study start until one of the following events occurs:

- $\geq 2$  new bone lesions on Technetium bone scan. If  $\geq 2$  new lesions are detected at or 12 weeks following initiation of treatment, progression must be confirmed by the presence of  $\geq 2$  or more additional lesions to rule out bone scan flare as a cause of the radiographic changes.

- RECIST-defined tumor progression.
- Clinical deterioration requiring a change in prostate cancer therapy, or at clinician discretion
- Surgery or Radiation to treat a prostate cancer related indication
- Death from any cause.

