#### **2.4.2 Secondary Endpoints**

- PSA decline of  $\geq 50\%$  at 12 weeks post therapy initiation
- Time to PSA progression. Defined as a rise in PSA of 50% above nadir value or 25% above baseline if there is no decline.
- Relationship of abiraterone resistance status (primary vs acquired) and outcome
- Time to confirmed development of  $\geq 2$  new bone lesions that cannot be attributable to bone scan flare
- Reduction in pain for symptomatic patients
- Safety
- Serum selinexor levels as a function of dose and time
- Pharmacodynamic analysis of selinexor impact on XPO-1 expression, leukocyte gene expression profile, and macrophage inhibitory cytokine-1 (MIC-1) mRNA expression

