## 6.1.1 Pretreatment Period

### 6.1.1.1 Screening Assessments

With the exception of CT or MRI imaging for the purposes of tumor/lesion assessment, all screening procedures and assessments must be completed within 28 days of the Day 1 Visit. Any requisite imaging must be obtained within 42 days of day 1 of study participation.

- Physical examination
- Vital signs
- Complete medical history
- Baseline conditions assessment
- ECOG Performance status
- Ophthalmologic exam including slit lamp examination and visual acuity prior to dilation, and a dilated fundoscopic evaluation and slit lamp examination.
- Neurological evaluation
- Pulse oximetry
- History of prior treatments and any residual toxicity relating to prior treatment
- Baseline medications taken within 28 days of Day 1
- Brief Pain Inventory (BPI) short form
- Laboratory evaluations
  - Complete blood count (CBC) with differential and platelet count and coagulation tests
    - Coagulation indices including international normalized ratio (INR), prothrombin time (PT) and activated partial thromboplastin time (aPTT) do not need to be repeated at screening if patients have already completed a biopsy through the companion radiologically guided mCRPC protocol or they have been deemed ineligible for biopsy.
  - Blood chemistry assessment, including:
    - Alkaline phosphatase, aspartate aminotransferase/alanine aminotransferase (ALT/AST), total bilirubin, calcium, phosphorus, blood urea nitrogen (BUN), creatinine, total protein, albumin, fasting glucose, potassium, sodium, chloride, bicarbonate, uric acid, lactate dehydrogenase (LDH), fasting lipid panel (low-density lipoprotein [LDL], total cholesterol, triglycerides)
  - Prostate Specific Antigen (PSA)
  - Serum total testosterone

- Imaging (CT or MRI) of chest, abdomen and pelvis for tumor/lesion assessment, contrast is to be used unless clinically contraindicated.
- Electrocardiogram (ECG)
- Bone scan (Technetium)
- Prophylactic therapy (initiated 0-3 days prior to first selinexor dose)
- Tumor biopsy -- optional, per companion Radiologically Guided Biopsy protocol of mCRPC, offered to patients treated at UCSF, UCLA, UC Davis, Oregon Health Sciences University, University of British Columbia

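### The week-16 endpoint list counts cancer pain needing opiates as an event without requiring it to be new, so the status of men already on opiates at entry is undefined

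*Combined protocol and SAP*

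**What the plan says.** Section 8.4.2 states: "The primary end point is proportion of patients without evidence of radiographic progression at 16 weeks". It introduces the event list with "This is defined from study start until one of the following events occurs", and one of the five items is "Cancer related pain requiring opiate analgesics". The item has no onset, escalation or baseline condition.

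Two other statements of the endpoint omit it. Section 2.4.1 has in its place "Clinical deterioration requiring a change in prostate cancer therapy, or at clinician discretion". The rPFS paragraph later in Section 8.4.2 also has no opiate item. Where there is no radiographic event, it says "rPFS will be defined as time from start of study until clinical deterioration requiring a change in prostate cancer therapy or at clinician discretion", and then adds surgery or radiotherapy and death.

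Nothing in Sections 3.3.1 and 3.3.2 bars pain or opiate use at entry. At least one bone metastasis is required. Pain is also an outcome: Section 2.2 has the objective "To determine the effect of selinexor on persistent pain associated with bone metastasis using the brief pain inventory (BPI) short form" and Section 2.4.2 the endpoint "Reduction in pain for symptomatic patients". Screening (Section 6.1.1.1) records "Baseline medications taken within 28 days of Day 1", and concomitant medications are recorded at Cycle 1 Day 1 and on Day 1 of each later cycle.

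**The concern.** The other items in the list are changes or discrete acts: new bone lesions, RECIST progression (measured against the smallest sum since treatment began), surgery or radiotherapy, and death. Pain that needs opiates is a state. It can exist before the first dose and continue unchanged after it. A man whose scans are clear at week 16 and whose pain has eased, but who is still on the opiate he came in with, meets the item as written.

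The week-16 count drives both decisions in Section 8.2.1: stop at 10 or fewer of 18, and reject the null at 36 or more of 54. If baseline users are scored as failures, the count depends partly on who enrolled and not only on what the drug did. If they are not, it does not. With no rule, two analysts could classify the same man in opposite ways. In a single-arm, open-label trial that choice should not be left until outcomes are known.

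**Working it through.** **Inputs from Section 8.2.1.** Stage 1: 18 patients, stop at 10 or fewer successes. Final: 54 patients, reject at 36 or more. Null rate 0.55, alternative rate 0.75.

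**Formulas (exact binomial).** With X1 the successes among the first 18 and X2 those among the next 36:
- P(stop at stage 1) = P(X1 ≤ 10)
- P(reject) = sum over x = 11 to 18 of P(X1 = x) × P(X2 ≥ 36 − x)

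**The plan's own figures.** At 0.55, P(stop) = 0.6085 and P(reject) = 0.0477. The plan states 60.9% and 0.048. At 0.75, P(reject) = 0.9007, against a stated 90.0%. The design reproduces.

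**Bounds on the literal reading, free of any assumed share or response rate.**
- Eight baseline users among the first 18 leave at most 18 − 8 = 10 successes, which is a stop.
- Nineteen among 54 leave at most 54 − 19 = 35, one short of 36.

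These bounds are rarely reached at low shares. The chance of eight or more among 18 is 0.0002 at a 10% share, 0.016 at 20% and 0.141 at 30%. At lower shares the loss comes from dilution of the success rate.

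**Dilution on the literal reading.** Let f be the share of men on opiates for cancer pain at entry. The documents give no value, so f is an assumption. Suppose all of these men are scored as failures and the others succeed at 75%. The observed rate is then 0.75 × (1 − f).

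| f (assumed) | Observed rate | P(stop at stage 1) | Power |
|---|---|---|---|
| 0% | 0.75 | 0.057 | 0.901 |
| 5% | 0.7125 | 0.115 | 0.764 |
| 10% | 0.675 | 0.201 | 0.562 |
| 15% | 0.6375 | 0.311 | 0.345 |
| 20% | 0.60 | 0.437 | 0.172 |

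A true 75% falls to the 55% null at f = 1 − 0.55/0.75 = 26.7%. The error runs against the drug: if the null rate shrinks in the same way, at f = 10% it becomes 0.55 × 0.90 = 0.495 and the type I error falls from 0.0477 to 0.0070.

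**Dependence on the men's own prognosis.** If baseline users would otherwise succeed at rate r, the item removes f × r from the overall rate. At f = 10% this is 7.5 percentage points if r = 0.75, and 5.5 points if r is, say, 0.55. The table therefore shows the case in which r equals the rate of the other patients.

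**New-onset reading.** Baseline users do not fail on this item for the opiates they entered on, f has no effect by this route, and the stated design stands.

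**The case against.** The strongest reply is that the lead-in already settles the matter. It speaks of events that occur from study start, which is the language of incidence. The surgery or radiotherapy item has no new-onset wording either, and exclusion 14 admits men whose single palliative fraction was given as little as 14 days before the first dose. Nobody would score that as a failure on day 1. This makes the new-onset reading a fair one, but it does not settle the point. Past radiotherapy is a completed act, whereas pain that needs opiates continues after study start and still satisfies the item. Nor does the new-onset reading say whether a baseline user is exempt or fails when his dose rises.

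Second, the item is in one of three statements of the endpoint, and the endpoint is named as radiographic. The problem disappears if the lists are aligned with Section 2.4.1. That stands, and it sets the order of the fix. However, the list with the opiate item is the one attached directly to the week-16 proportion, so it cannot be disregarded.

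Third, the number of such men may be small. Entry requires ECOG 0 or 1 and no chemotherapy for mCRPC, and men who urgently need docetaxel are excluded. That also stands: opiate users can enrol, but the documents do not show how many will.

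A reader might also infer that all the symptomatic men in whom pain relief is to be studied would be scored as failures. The documents do not support this. The pain objective and endpoint concern men with pain, and the event requires pain that needs opiates. Symptomatic men on no analgesic or on non-opiates do not meet it.

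**Conclusion.** The plan leaves men on opiates for cancer pain at entry without a defined status on the primary endpoint. On the literal reading each one is a failure whatever the drug does; on the new-onset reading he is not. A reader might infer that the plan rules such men to have failed on day 1. It contains no such rule, and its lead-in supports the other reading too.

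The fall in power to 0.76, 0.56 and 0.17 at shares of 5%, 10% and 20% holds only on the literal reading. It rests on four assumptions:
- the share itself, which no section gives;
- baseline users otherwise matching the 75% rate;
- the 75% having been set without this item, since the plan does not say which event list underlies its 55% and 75%;
- every man in the share taking opiates for cancer pain.

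The figures show sensitivity and are not a forecast. The two bounds, 8 of 18 and 19 of 54, need only the literal reading. Because the ambiguity feeds both decision rules, it should be settled before the stage 1 count is made.

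**What to change.** First reconcile the three statements of the endpoint (Section 2.4.1, the Section 8.4.2 list and the Section 8.4.2 rPFS paragraph), and record which one the 55% and 75% refer to.

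If the opiate item is dropped to match Section 2.4.1, nothing more is needed on this point.

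If it is kept, define it as the start of opiate analgesics for cancer pain after the first dose, in patients not taking opiates for cancer pain at baseline. For those who are, let the remaining components decide week-16 status. Baseline use can be identified from the screening medication record, and new use from the concomitant medication records. Confirm that the case report form captures the indication, because the schedule lists the medications but does not say that the reason for them is recorded.

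The cost is one sentence in Section 8.4.2 and possibly one data field. The downside is that worsening pain in baseline opiate users is then caught only through the other components.

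### The week-16 progression-free count that drives both decision rules has conflicting event definitions and no rule for patients whose week-16 status is unknown

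*Combined protocol and SAP*

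**What the plan says.** Section 8.4.2 makes the primary endpoint the proportion of patients without radiographic progression at 16 weeks. It adds "This is defined from study start until one of the following events occurs" and lists five events: two or more new bone lesions, RECIST progression, "Cancer related pain requiring opiate analgesics", surgery or radiation for prostate cancer, and death.

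The next paragraph of 8.4.2 defines rPFS again: "Radiographic PFS will be defined as the time from treatment initiation to the occurrence of either tumor progression in soft tissue", or two or more new bone lesions confirmed at least 12 "weeks later). If no such event exists, then rPFS will be defined as time from start of study until clinical deterioration", surgery or radiation, or death. It then gives a censoring rule, "PFS will be censored at the last scheduled disease assessment on study", ahead of the Kaplan-Meier analysis.

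Section 2.4.1 also defines rPFS as the primary endpoint. It has no opiate event, includes "Clinical deterioration requiring a change in prostate cancer therapy, or at clinician discretion", and says that if two or more "new lesions are detected at or 12 weeks following initiation of treatment, progression must be confirmed by the presence of" at least two additional lesions.

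Section 7.3 requires new lesions on the week-8 bone scan to be rescanned at least six weeks later. Two or more further lesions then make it progression, dated back to week 8. Findings on later scans need no confirmation.

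Sections 8.2.1 and 8.3 use the week-16 count (10 or fewer of 18; 36 or more of 54; 55% against 75%) without citing any of these definitions. The Abstract and section 3.2 speak of 54 evaluable patients, while 8.4.1 bases all analyses on all treated patients.

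**The concern.** Each decision turns on a count, and one patient separates 10 from 11 of 18 or 35 from 36 of 54. Two analysts following different sections could classify the same patient differently, and nothing in the plan would settle it. If the choice is made after the stage 1 data are seen, the error rates in 8.2.1 no longer describe the trial.

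Unknown status is foreseeable. Patients removed for adverse events are not replaced (8.2.2). Neither the end-of-treatment visit (6.1.3) nor the telephone follow-up (6.1.4) includes imaging. A patient who stops for toxicity at week 6 therefore has no scheduled week-16 scan, and the plan does not say whether he counts as a success, counts as a failure or is left out.

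**Working it through.** **1. The definitions side by side**

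| | 8.4.2 bullets | 2.4.1 | 8.4.2 paragraph | 7.3 (bone only) |
|---|---|---|---|---|
| Opiate-requiring pain | event | not listed | not listed | – |
| Clinical deterioration or clinician discretion | not listed | event | event, conditional | – |
| Bone confirmation | none stated | ≥2 additional lesions, timing unclear | ≥12 weeks later | week-8 findings only, ≥6 weeks later, back-dated |
| Which event counts | first to occur | first to occur | scan event; others only if there is none | – |

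RECIST progression, surgery or radiation, and death are in all three full lists. Read literally, the last row lets a later scan finding displace an earlier clinical event.

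**2. A patient the rules classify differently.** Bone scans fall at weeks 8, 16, 24 and every 12 weeks thereafter (8.4.3). Take two new lesions at week 8 and none added at week 16.
- Bullets read literally: failure.
- 7.3: confirmation is possible from week 8 + 6 = 14, so the week-16 scan serves. No lesions were added, so this is not progression.
- 8.4.2 paragraph, if applied to the count: confirmation is possible only from week 8 + 12 = 20, and the next scheduled scan is week 24. Status at week 16 is unresolved.

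**3. The stated design.** Inputs from 8.2.1: n1 = 18, stop if ≤10; N = 54, reject if ≥36; p0 = 0.55, p1 = 0.75.

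P(early stop) = P(X1 ≤ 10), with X1 ~ Bin(18, p).
P(reject) = Σ over x = 11 to 18 of P(X1 = x) × P(Bin(36, p) ≥ 36 − x).

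Results: early stop under the null 0.6085 (stated 60.9%), type I error 0.0477 (stated 0.048), power 0.9007 (stated 90.0%). All three reproduce.

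**4. Unknown status.** The documents give no missing rate, so m = 5% and 10% are assumptions, with missingness unrelated to true status. The cut-offs are unchanged.

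Counted as not progression-free, p becomes p(1 − m):
- m = 5%: p0 = 0.55 × 0.95 = 0.5225, type I error 0.020; p1 = 0.75 × 0.95 = 0.7125, power 0.76.
- m = 10%: p0 = 0.495, type I error 0.007; p1 = 0.675, power 0.56.
- On average 1, 2 or 3 of 54 missing (m = k/54): p1 = 0.736, 0.722, 0.708; power 0.86, 0.81, 0.74.

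Counted as progression-free, p becomes p(1 − m) + m:
- m = 5%: p0 = 0.5225 + 0.05 = 0.5725, type I error 0.090.
- m = 10%: p0 = 0.495 + 0.10 = 0.595, type I error 0.154.

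**The case against.** The best defence is that 8.4.2 already separates two quantities: the bullets belong to the week-16 proportion, and the paragraph defines time-to-event rPFS for Kaplan-Meier. Section 7.3 can then be read as the working rule for bone scans, so the bullets' silence on confirmation contradicts nothing. The timing phrase in 2.4.1 appears to lack a word, possibly lost in text extraction. If it was meant to cover scans up to week 12, week 8 is the only scheduled scan affected, and 2.4.1 and 7.3 largely agree.

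Much of this stands, and it narrows the firm bone conflict to the 12-week phrase. It does not reconcile the event list in 2.4.1 with the bullets, and no section says that the bullets or 7.3 govern the count.

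On the denominator, 8.4.1 points to all treated patients, and 8.2.2 rules out replacing patients removed for adverse events. That largely settles who is counted, although the word evaluable remains in the Abstract and 3.2. It does not settle how an unknown is counted. One could argue that a patient never classified as progression-free fails by default, but the plan does not say so.

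A reader might also infer that the two visit windows (±3 days in 6.1, ±7 days in Table 6.1) threaten the six-week rescan interval. They do not: scans have their own Day 22–28 window, which puts them on study days 50–56 and 106–112, so the gap is 106 − 56 = 50 to 112 − 50 = 62 days, always above 42. Nor is any effect on the count shown from the difference between study start and treatment initiation as time origin.

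**Conclusion.** The point holds. The primary count lacks a single event definition and a rule for unknown status, and both must be fixed before the 18-patient look.

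The arithmetic in 8.2.1 is sound. A reader might infer that the stated error rates are miscalculated or that the trial must be enlarged; the documents support neither. The 0.048 and 90.0% are correct for a count made under one definition with no missing status.

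The size of the effect rests on assumed missing rates of 5% and 10%. Within that range, the unwritten choice can leave power as low as 0.56 or raise type I error as high as 0.154. The effect of the event-list conflict cannot be sized from the documents, and its net direction is unknown. The documents also do not say which event list underlies the 55% and 75% rates.

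**What to change.** Reconcile 2.4.1 and 8.4.2 before the first-stage look:

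- **One event list.** The default is the one shared by 2.4.1 and the 8.4.2 paragraph: bone progression, RECIST progression, clinical deterioration or clinician discretion, surgery or radiation, and death. The team must confirm that it matches the list behind 55% and 75%.
- **One bone rule.** The default is the existing rule in 7.3. Repair the timing phrase in 2.4.1 to match, and delete the 12-week confirmation from 8.4.2.
- **Earliest event.** Define the endpoint as time to the earliest listed event, and delete the clause that counts clinical events and death only when there is no scan event.
- **Denominator.** State that this definition drives both the 18- and 54-patient counts among all treated patients, and remove the word evaluable from the Abstract and 3.2.
- **Unknown status.** Count it as not progression-free. Keep censoring for Kaplan-Meier only.

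This changes wording and adds no scans. The cost is power: under the missing-status rule the stated 90.0% holds only with complete data. It should be qualified with the figures above, for example 0.86, 0.81 or 0.74 when 1, 2 or 3 of 54 patients lack status on average. Patients who stop early without a week-16 scan will count against the drug. In exchange, under the assumed missingness, type I error stays below the stated 0.048.

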### 3.4 Duration of Therapy

In the absence of treatment delays due to adverse events, treatment may continue until:

- Disease progression
- Inter-current illness that prevents further administration of treatment
- Unacceptable adverse event(s), including any occurrence of grade 4 neurotoxicity
- Patients decides to withdraw from the study
- Significant patient non-compliance with protocol
- General or specific changes in the patients' condition render the patient unacceptable for further treatment in the judgment of the investigator.

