### 3.5 Duration of Follow Up

Patients will be followed for 30 days after completion of treatment or removal from study, or until death, whichever occurs first. Patients removed from study for unacceptable treatment related adverse event(s) will be followed until resolution or stabilization of all treatment related adverse events to Grade 2 or lower.

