**Table 6.1 Schedule of Study Procedures and Assessments**

Visits must occur ±7 days of planned visit unless otherwise noted.

Period/ Procedure	Screening				Cycle 1		Cycle 2 and future Cycles	End of Treatment visit	Follow- up visits
	-28 to 0	1	3 	15	1	1	Within 30 days of last dose	By phone Every 6 months	
Treated leukocyte lysate 		X							
Serum MIC-1 mRNA 		X		X	X				
Selinexor PK 		X							
Testosterone	X								
Imaging procedures									
CT c/a/p with contrast or MRI	X					X 			
ECG/EKG	X								
Bone scan (Technetium)	X					X 			

 Required at screening and as clinically indicated while on study. Coagulation labs include PT, PTT/INR.

 Only offered to patients at UCSF, UCLA, UC Davis, Oregon Health Sciences University, University of British Columbia. If no intervening therapy is initiated, the tumor biopsy can be performed within a 2-month window (60 days) of day 1 of Selinexor.

 Including alkaline phosphatase, ALT/AST, total bilirubin, calcium, phosphorus, (BUN), creatinine, total protein, albumin, fasting glucose, potassium, sodium, chloride, bicarbonate, uric acid, LDH, fasting lipid panel (LDL, total cholesterol, triglycerides).

 Monthly and at time of progression

 Only Cycle 2 and Cycle 4, Day 22-28, and at time of progression

 PK samples will be collected on Cycle 1 Day 1 only. PD Samples will be collected on Cycle 1 Day 1 and 15, Cycle 2 Day 1, and cycle 3 Day 1. Refer to section 6.3 for PK and PD collection schedule.

 At the completion of Cycle 2, Cycle 4, Cycle 6, Day 22-28, and every 12 weeks thereafter

 Required at screening, every 3 months thereafter if cataracts identified at screening and if clinically indicated, and at the end of treatment study visit.

 C1D3 visit will be conducted via telephone call

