#### Time to confirmed development of $\geq 2$ new bone lesions

Time to development of  $\geq 2$  new bone lesions, defined as the time interval between the date of treatment initiation and the date of documented new lesions. Bone scans will be performed at week 8, 16, 24, and every 12 weeks thereafter; evaluation criteria is defined by the PSAWG2 criteria for bone scan evaluation. The time will be 'backdated' to when the  $\geq 2$  new lesions were detected if a second scan is done to confirm progression.

Kaplan-Meier methods will be used to estimate the median time to development of  $\geq 2$  new bone scans with a 95% confidence interval.

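### The rPFS censoring date is tied to the last scheduled assessment, which can be read as crediting unobserved time; separately, the 16-week count has no rule for a patient who was not scanned

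*Combined protocol and SAP*

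**What the plan says.** Section 8.4.2 gives one general censoring rule for patients without an event: "PFS will be censored at the last scheduled disease assessment on study". It adds a special case: "PFS of living patients with no assessment on-study, and PFS of patients with no baseline assessment will be censored at enrollment". No other section defines the censoring date or says how a missed scan is handled.

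The rule acts on the time-to-event analysis: "rPFS will be estimated using the Kaplan-Meier product limit method". The outputs are the median, the rates at 6 and 12 months, and the Cox comparison of primary with acquired resistance in Section 8.4.3.

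Scans are spaced 8 weeks apart to week 24 and 12 weeks apart afterwards. Section 8.4.3 says "Bone scans will be performed at week 8, 16, 24, and every 12 weeks thereafter", and footnote 7 of Table 6.1 gives the same timing by cycle: "At the completion of Cycle 2, Cycle 4, Cycle 6, Day 22-28, and every 12 weeks thereafter".

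The formal test uses a different quantity: "The primary end point is proportion of patients without evidence of radiographic progression at 16 weeks". Sections 8.2.1 and 8.3 count successes at that time point. The trial stops at 10 or fewer of 18, and the null is rejected at 36 or more of 54.

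**The concern.** Scheduled is not the same as performed. A patient scanned clear at week 8, who misses week 16 and is never scanned again, was last known to be progression-free at week 8. On the literal wording he is censored at week 16. He then sits in the week-16 risk set without being able to contribute an event there, so the Kaplan-Meier curve drops by too little.

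The design makes such patients foreseeable. Section 3.4 lets treatment end for toxicity, non-compliance or withdrawal ("Patients decides to withdraw from the study"). The end-of-treatment visit in Section 6.1.3 lists no CT, MRI or bone scan. Section 3.5 says "Patients will be followed for 30 days after completion of treatment or removal from study, or until death, whichever occurs first", and the later contacts in Section 6.1.4 are by telephone. Two programmers could in good faith date the same patient 8 or 12 weeks apart.

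The 16-week count has a related but separate gap. Its wording rests on absence of evidence of progression, and a patient who was not scanned has no such evidence.

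**Working it through.** **1. The plan's own design figures.** Inputs (Section 8.2.1): n1 = 18, stop at 10 or fewer; N = 54, reject at 36 or more; p0 = 0.55, p1 = 0.75.

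P(reject | p) = Σ over x = 11 to 18 of Bin(x; 18, p) × P[Bin(36, p) ≥ 36 − x]

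- p = 0.55: 0.0477 (stated 0.048); early stopping 0.6085 (stated 60.9%)
- p = 0.75: 0.9007 (stated 90.0%)

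All three reproduce. No censoring date enters this formula, so the censoring sentence cannot change these figures.

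**2. A small example of the censoring effect.** The counts are invented. Of 54 patients, 14 progress at week 8. Of the other 40, 6 miss week 16 and are not scanned again, and 9 of the 34 scanned progress.

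- Censored at last performed scan: (40/54) × (25/34) = 0.545
- Censored at the missed scan: (40/54) × (31/40) = 0.574

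The difference is 2.9 points.

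**3. A range.** The documents give no loss rate, so 10, 20 and 30% loss without an event by week 16 is assumed. Loss and progression are taken as exponential and independent, with the protocol's scan schedule. The table credits every lost patient to the next scheduled scan (simulation of 400,000 patients).

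| Week-16 Kaplan-Meier | Last performed | Literal, 10 / 20 / 30% loss |
|---|---|---|
| Null | 0.55 | 0.569 / 0.592 / 0.614 |
| Alternative | 0.75 | 0.762 / 0.775 / 0.787 |

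That is about +2 to +6 points at the null and +1 to +4 at the alternative.

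These figures also credit patients lost before week 8, whom the special-case sentence sends to enrollment. Applying that sentence leaves the week-8 step unbiased. Let q be the probability of remaining progression-free over 8 weeks and g the probability of not being lost over 8 weeks. Then

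S(16) = q × [1 − g(1 − q)]

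- Null, q = √0.55 = 0.7416. At 10% loss g = √0.9 = 0.9487, so S = 0.7416 × 0.7549 = 0.560. At 30% loss g = √0.7 = 0.8367, so S = 0.7416 × 0.7838 = 0.581.
- Alternative, q = √0.75 = 0.8660. S = 0.8660 × 0.8729 = 0.756 at 10% loss and 0.8660 × 0.8879 = 0.769 at 30%.

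With both sentences applied, the week-16 shift is therefore about +1 to +3 points at the null and +1 to +2 at the alternative.

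The plan reports 6 and 12 months. On this schedule the curve is flat from week 24 to 36 and from week 48 to 60, so those rates are the week-24 and week-48 values. At the null:

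- 6 months: S(24) = q × [1 − g(1 − q)]². Last performed 0.55^1.5 = 0.408; literal 0.7416 × 0.7549² = 0.423 to 0.7416 × 0.7838² = 0.456.
- 12 months: multiply by [1 − g₁₂(1 − q₁₂)]², where q₁₂ = 0.55^0.75 = 0.6387 and g₁₂ = 0.9^0.75 = 0.9240 or 0.7^0.75 = 0.7653. Last performed 0.55³ = 0.166; literal 0.4226 × 0.6661² = 0.188 to 0.4556 × 0.7235² = 0.238.

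If patients lost before week 8 are credited too, the week-24 range is 0.43 to 0.48 and the week-48 range 0.19 to 0.25.

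**4. The 16-week count.** Assume a fraction m has no week-16 scan, unrelated to true status.

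- Counted as successes, null rate = 0.55 + 0.45m. m = 5%: 0.5725, P(reject) = 0.090. m = 10%: 0.595, P(reject) = 0.154.
- Counted as failures, alternative rate = 0.75 × (1 − m). m = 5%: 0.7125, power = 0.764.

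**The case against.** The plan never says scheduled whether or not performed. Scheduled can mean a protocol-planned assessment, as opposed to an unscheduled one, that took place. The special-case sentence supports this. Under the literal reading, a patient who missed only week 16 would be credited to week 16, while one who missed every scan would be credited nothing. The words on study also help, since a patient who has left arguably has no further assessments scheduled on study. So a reader might infer that the plan adopts a rule crediting unobserved time, and the text does not support that. It supports only an ambiguous date. The ambiguity still stands, because the special case does not reach a patient with one or more scans followed by a missed last one.

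A missed scan adds time only if no later scan follows. A patient who misses week 16 but is scanned at week 24 is unaffected.

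A reader might also infer that six unscanned patients add 6/54 = 11 points to the primary result through this sentence. They do not, because the binary count uses no censoring date. Any such effect would come from the separate classification gap.

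Finally, Section 8.4.2 already counts clinical deterioration requiring a change of therapy, surgery, radiation and death as events. Many failing patients who miss scans would therefore be events, which limits how informative the missed scans are.

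**Conclusion.** The censoring date is ambiguous, and the literal reading biases the rPFS curve upward. The size depends on an assumed loss rate. For 10 to 30% lost by week 16, the week-16 shift at the null is about 2 to 6 points if every lost patient is credited to the next scan. It is about 1 to 3 points once patients with no on-study assessment are censored at enrollment. The shift is zero if the last scheduled scan was done.

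The 6- and 12-month rates are exposed. The median is exposed in principle but moves only in scan-interval steps: with both sentences applied, it stays at week 24 (null) and week 48 (alternative) in these scenarios. The Cox comparison in Section 8.4.3 is also exposed. The direction of any error in its hazard ratio depends on which resistance group misses more final scans.

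The 10/18 and 36/54 rules are not affected by the censoring sentence. Their own gap, the unscanned patient at week 16, can matter more: alpha of 0.090 or 0.154 in place of 0.048 if 5% or 10% are counted as successes. Those fractions are assumptions, and the plan does not say that it would count patients this way.

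**What to change.** In Section 8.4.2, replace the censoring sentence with: *PFS will be censored at the date of the last adequate disease assessment actually performed that showed no progression.* Keep the special case for patients with no on-study or no baseline assessment.

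For the 16-week count, add to Sections 8.2.1 and 8.4.2: *A patient with no assessment at week 16 or later showing no progression is not counted as progression-free at 16 weeks.* The words or later keep a patient who missed week 16 but was clear at week 24 as a success.

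The cost is two sentences. If performed assessments were always meant, the first changes nothing; otherwise the reported rates may be slightly less favourable. The second costs power: 90% falls to about 76% if 5% are unassessed and counted as failures, so week-16 scans need to be obtained. The first sentence removes credited time but does not cure informative loss, so the number of patients censored after a missed scan should be reported.
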